These inclusion/exclusion criteria were chosen so that the study has as much real world applicability as possible, while also minimizing risks to subjects. Based on our preliminary data, we believe that with these inclusion and exclusion criteria, and accounting for subjects who don't want to participate and also dropout, we will still be able to recruit enough subjects to meet our recruitment goals within 2 years.

Sample Size:

We have specifically designed this as a pilot study due to lack of data to help inform sample size calculations. However, hypothesizing a difference between VM-PATHI scores between groups of 7 points, and using the standard deviation from the validation of the instrument, we with 50 subjects total, or 25 per arm, we will have 90% power to detect a significant difference at the 0.05 level between groups to assess the efficacy of galcanezumab for vestibular migraine. If we assume a 10% dropout rate in the trial we will still have greater than 80% power to detect a difference.

Clinical Sites:

We will perform this study as a single center. We will be recruiting subjects from both the Otolaryngology-Head and Neck Surgery and Neurology departments. In a previous study where we developed the VM-PATHI, we were able to recruit around 80 subjects with vestibular migraine in a little over 1 year.

Study Visit Timeline:

The study visits will be scheduled within +/- 4 days of the expected timeline. This flexibility is based on the clinic availability dates of the PI and other providers.

- Study Visit 1 (SV1) = Day 0 / Month 0
- Study Visit 2 (SV2) = Day 30 / Month 1
- Study Visit 3 (SV3) = Day 60 / Month 2
- Study Visit 4 (SV4) = Day 120 / Month 4

Re-Enrollment Policy:

For participants who met all inclusion criteria AND none of the exclusion criteria (except for not having the minimum required VM-PATHI score and/or definitive dizzy days), they can re-enroll in the study at a later date when they feel their symptoms are worse. At that time, the participant would have to start over from Day 0 and undergo screening again.

Randomization:

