Dizziness Handicap Inventory (DHI): This is the most widely used measure of dizziness severity, and consists of 25 questions. Questions ask about problems related to dizziness, and are scored as no (0 points), sometimes (2 points), or always (4 points). Total score is between 0 and 100, with higher scores indicating more disability. While subjects with vestibular migraine suffer from a variety of symptoms, dizziness is clearly the predominant feature. Furthermore, this will help us compare data to other studies that involve causes of dizziness.

PROMIS SF v1.2- Global Health: This is a widely used and validated quality of life measure. It is quick and simple to administer. There are 10 questions on this scale, each with a score of 1-5. Higher scores correspond to a greater extent of the concept measured (e.g., more fatigue, more pain). Two summed scores are generated, one for global mental health (question #3, 6, 7, 8) and one for global physical health (question #2, 4, 5, 10). The remaining 2 questions are analyzed separately. Summed scores for global physical health and global mental health are converted into T-score values using the "HealthMeasures Scoring Service" (https://www.assessmentcenter.net/ac_scoringservice). The T-scores for physical health and mental health can then be grouped into excellent, very good, good, fair, and poor categories. The cut points for each category is determined by calculating the midpoint between 2 adjacent means. For example, if the mean mental health T-score for “Excellent” is 61 and the mean mental health T-score for “Very Good” is 51, then the cut point for these categories would be a T-score of 56.

Data Collection:

Data collection will be performed by the clinical research coordinator during each study visit. This data will be entered into the REDCap database by the research coordinator. VM-PATHI, DHI, GAD-7, PHQ-9, PROMIS SF v1.2- Global Health, and HIT-6 will be administered electronically via REDCap to the subject during the study visit. The schedule of collection of each data point is reviewed in appendix 1. The data collection instructions are contained within appendix 2.

Stopping Rules:

There will be no stopping rules for this trial, given the short duration of the study. Each adverse effect and serious adverse effect will be reviewed by the data safety monitoring team, and subjects may be unblinded and/or the study will be stopped early for serious safety concerns.

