The active drug and placebo will be managed through the research pharmacy at UCSF. The drug and placebo will be supplied by Eli Lilly and Company. Study drugs will be given to patients on the day of randomization (month 1), so any failure of subjects to take the study drugs will just be considered a violation of protocol, but they will be included in the intent to treat analysis.

Packaging:

Study drug will be supplied in preloaded syringes, each with a dose of 120 mg or placebo. Subjects will first receive the first month's supply (240 mg or placebo) at study visit 2, and then will receive a two-month supply at study visit 3. So, at study visit 2 and 3, each participant will get two pre-filled syringes. They will also get an insulated bag with a cold pack to keep the drug cool until it can be refrigerated at home.

Labeling:

Each carton (kit) of study drug will be labeled with the required FDA warning statement, the protocol number, a treatment number, the name of the sponsors, and directions for patient use and storage.

Dosage:

The study drug will be administered in fixed dose of 120 mg. The first administration, at month 1, will be a loading dose of 240 mg. Each subsequent injection (month 2 and 3) will be 120 mg dose. There will be no dose adjustment for weight, age, or any other factors

Dispensing of Study Drug:

Drugs will be administered in a packet with a 1-month supply by the site investigator at study visit 2. They will then get the second 2-month supply at study visit 3.

Administration of Study Drug:

Subjects will self-administer the drug, with a pre-filled syringe, into an acceptable area of the body. This is typically the thigh, but also includes the abdomen, buttocks, or back of the upper arm. Study personnel will monitor with first and second injection to ensure compliance and proper administration. A note will be placed into the medical record confirming the time, date, and location of the injection (part of the body). For the third injection, the CRC will reach out to the patient to confirm injection, and then record time, date, and anatomic site of the injection. Adherence to the injection will be confirmed by asking participants to send the CRC a picture of the empty syringe. This picture will be uploaded to the REDCap record.

Storage of Study Drug:

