The Investigator will probe, via discussion with the subject, for the occurrence of AEs during each subject visit and record the information in the site's source documents. Adverse events will be recorded in the patient CRF. Adverse events will be described by duration (start and stop dates and times), severity, outcome, treatment and relation to study drug, or if unrelated, the cause.

g. Serious Adverse Experiences (SAE):

SAE is defined as any AE occurring at any dose that results in any of the following outcomes:

- Death

- A life-threatening adverse experience
- inpatient hospitalization or prolongation of existing hospitalization
- A persistent or significant disability/incapacity
- A congenital anomaly/birth defect
- Other important medical events may also be considered an SAE when, based on appropriate medical judgment, they jeopardize the subject or require intervention to prevent one of the outcomes listed

Serious Adverse Experience Reporting:

Study sites will document all SAEs that occur (whether or not related to study drug) per UCSF CHR Guidelines. The collection period for all SAEs will begin after informed consent is obtained and end after procedures for the final study visit have been completed. In accordance with the standard operating procedures and policies of the local Institutional Review Board (IRB), the site investigator will report SAEs to the IRB.

Privacy Protection:

The study will be conducted according to the Declaration of Helsinki, Protection of Human Volunteers (21 CFR 50), Institutional Review Boards (21 CFR 56), and Obligations of Clinical Investigators (21 CFR 312).

Clinical information will not be released without written permission of the subject, except as necessary for monitoring by the FDA. The Investigator must also comply with all applicable privacy regulations (e.g., Health Insurance Portability and Accountability Act of 1996, EU Data Protection Directive 95/46/EC).

Protocol Amendments:

Any amendment to the protocol will be written by the PI. Protocol amendments cannot be implemented without prior written IRB approval except as necessary to eliminate immediate safety hazards to patients. A protocol amendment intended to eliminate an apparent immediate hazard to patients may be implemented immediately, provided the IRBs are notified within five working days.

IRB:

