Appendix 1: Schedule of study events

Study month	0	1	2	3	4
Clinical Visit	✓ (L5) SV 1	✓ (L4) SV 2	✓ (L4) SV 3		✓ (L4) SV 4
Phase of study	Baseline Eval	Randomize/Start Treatment	First eval on Tx		Final eval for data/safety
Testing	CBC	✓			✓
	CMP	✓			✓
	EKG	✓			✓
	Pregnancy Test	✓			
	Audio (if not previously done)	✓			
	Vital signs	✓	✓	✓	✓
Questionnaires	VM-PATHI	✓	✓	✓	✓
	DHI		✓	✓	✓
	HIT-6		✓	✓	✓
	PROMIS SF v1.2- Global Health		✓		✓
	Med review	✓	✓	✓	✓
	Adverse Effects			✓	✓
	Medical history	✓			
	Demographics	✓			
	PHQ-9		✓		✓
	GAD-7		✓		✓

	Diagnosis form	√				
	Close-out form					√
Definitive Dizzy Day Text		√	√	√	√	√
Treatment			240 mg Emgality/Placebo	120 mg	12 0 mg	

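### Appendix 1 schedules adverse-effect entry only at SV3 and SV4, while the text requires it at every visit and SAEs from consent; separately, the last 60 of 90 on-treatment days have a single scheduled inquiry

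*Combined protocol and SAP*

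**What the plan says.** - **Adverse Events:** "The Investigator will probe, via discussion with the subject, for the occurrence of AEs during each subject visit". The same section wants each event described by start and stop dates and times, severity, outcome, treatment and relation to study drug.
- **Serious Adverse Experience Reporting:** "The collection period for all SAEs will begin after informed consent is obtained and end after procedures for the final study visit have been completed". This period is stated for SAEs only.
- **Data Collection:** "The schedule of collection of each data point is reviewed in appendix 1".
- **Appendix 1:** the "Adverse Effects" row is blank at SV1 and SV2 and ticked at SV3 and SV4.
- **Study Visit Timeline:** "Study Visit 2 (SV2) = Day 30 / Month 1" and "Study Visit 3 (SV3) = Day 60 / Month 2"; SV4 is day 120. There is no visit at month 3, although doses fall at months 1, 2 and 3.
- **Administration of Study Drug:** staff monitor the first and second injections. After that, "For the third injection, the CRC will reach out to the patient to confirm injection", and the coordinator records its time, date and body site. No AE question is listed.
- **Secondary Efficacy Endpoints:** the daily text asks about dizziness and, if there is any, about medication taken for it. It does not ask about AEs.
- **Data Safety Monitoring Plan:** the DSMB reviews SAEs within 5 days.

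**The concern.** There are two separate problems.

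**The text and the schedule disagree.** The investigator is told to ask at every visit. The schedule that lists the timing of data points prompts an entry at only two of the four. If staff work from the schedule, SV1 and SV2 produce no AE or SAE entry. SV2 is where randomization and the first, staff-monitored injection take place. Subjects who sign consent and then fail at SV1 or SV2 never reach a ticked visit, although SAE collection has begun for them.

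**The calendar leaves a long stretch with one inquiry.** After SV3 nobody is scheduled to ask about AEs until SV4, and two of the three dosing occasions have SV4 as their next inquiry. Mild or short-lived events are harder to recall and to date to the required standard after that interval. An SAE after day 60 that is not reported spontaneously may first come to light at SV4, which sits badly with a 5-day DSMB review. The protocol does not say whether those 5 days run from the event or from awareness of it.

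At stake is the completeness of the AE tables by arm, which are the trial's safety output, and how soon events become known.

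**Working it through.** **Reading the Appendix 1 row.** The table was broken in extraction, so the alignment was checked against neighbouring rows. Vital signs and VM-PATHI each show four ticks for the four visits. DHI shows one blank, then three ticks. The AE row shows two blanks, then two ticks. In four visit columns those ticks fall on SV3 and SV4.

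**Inputs.** Visits on days 0, 30, 60 and 120, each within 4 days (Study Visit Timeline). Doses on days 30, 60 and 90 (Intervention). Per-protocol windows (Data Analysis Plan): SV2 on days 23 to 44; SV3 23 to 37 days after SV2; SV4 50 to 70 days after SV3; day-90 injection 23 to 37 days after SV3.

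**The plan's own figure.** SV3 to SV4 = 120 − 60 = 60 days, which agrees with the Data Analysis Plan. With the 4-day windows the range is 116 − 64 = 52 to 124 − 56 = 68. The per-protocol window is 50 to 70.

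**Lag from each dose to the next scheduled AE inquiry** (day of inquiry − day of dose):

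| Dose day | As scheduled | With a question at the day-90 contact |
|---|---|---|
| 30 | 60 − 30 = 30 (SV3) | 30 (SV3) |
| 60 | 120 − 60 = 60 (SV4) | 90 − 60 = 30 (contact) |
| 90 | 120 − 90 = 30 (SV4) | 30 (SV4) |

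Under the per-protocol windows the day-90 dose has 50 − 37 = 13 to 70 − 23 = 47 days to SV4.

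**Share of treatment time resting on SV4 alone.** On-treatment time = 120 − 30 = 90 days. Days 60 to 120 = 60 days. 60/90 = 67%.

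**Consent to first scheduled entry.** 60 − 0 = 60 days, or 23 + 23 = 46 to 44 + 37 = 81 under the per-protocol windows. Half of the nominal 60 days is before treatment. With an inquiry at SV2 the interval is 30 days (23 to 44).

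**After the change.** Scheduled inquiries after the first dose rise from 2 to 3. The longest nominal on-treatment recall falls from 60 to 30 days. If the contact takes place on the injection day, the longest recall under the per-protocol windows is 25 days (SV4 at 50, contact at 25) to 47 days (SV4 at 70, contact at 23), instead of 50 to 70.

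**Would reconciling the ticks close the 60-day gap?** No. There is no month 3 visit, so asking at every visit still leaves nothing between day 60 and day 120. The two problems need separate changes.

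**The case against.** **The schedule need not override the text.** Data Collection only points to Appendix 1, and the AE row sits among the questionnaires. An investigator who follows the Adverse Events section will ask at every visit. This stands: the documents do not say that nothing will be recorded at SV2. They give two instructions that differ, and the shorter one is the one used for prompting.

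**SV3 and SV4 are the only visits that begin after dosing.** The protocol ties an AE to administration of the product, so ticks there fit its definition. This stands in part. It explains the blank cell at SV1 for ordinary AEs. It does not explain SV2, where dosing starts, and it does not meet the express rule that SAE collection starts at consent.

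**SV4 is not the only possible source.** Staff are present at the SV3 injection, SV3 has an AE tick, subjects may report spontaneously, and there is an early discontinuation visit. This is right. SV4 is the only scheduled inquiry after SV3, and nothing more is claimed.

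**Stronger readings.** A reader might infer that symptoms present before treatment could not be told from treatment-emergent ones. The documents do not support that: onset dates and times are required, injection times are recorded, and medical history, medication review, laboratory tests and several questionnaires precede treatment. A reader might also infer biased AE comparisons. In a double-blind trial with the same schedule in both arms, under-recording would be expected in both, and no differential loss is shown. Nor can the under-recording be expressed as a percentage, because the documents give neither an expected AE rate nor a recall rate.

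**Conclusion.** The inconsistency is real: the text requires AE inquiry at every visit and SAE collection from consent, and Appendix 1 prompts entry only at SV3 and SV4. For ordinary AEs the conflict is with the every-visit rule; the consent rule concerns SAEs. If the schedule alone is followed, SAEs between consent and SV2 (including those in subjects who then fail screening) have no prompted entry, and a reaction to the first injection has none until SV3, 30 days later.

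The long recall interval is a separate weakness of the visit calendar: 60 days for the day-60 dose, about 30 days for the day-90 dose, and 67% of on-treatment time resting on SV4.

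The likely cost is lower absolute AE rates, poorer dating and later detection, in both arms. The primary endpoint is not affected. The point should be corrected, but it does not threaten the trial's validity.

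This rests on two readings: that the AE ticks align with SV3 and SV4, and that the third injection means the day-90 dosing occasion. The loading dose is itself two injections, so the protocol's numbering is loose; the Data Analysis Plan's day-90 injection supports the second reading.

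**What to change.** 1. In Appendix 1, add AE/SAE entries at SV1 (for SAEs after consent) and at SV2, so that the schedule agrees with the Adverse Events and SAE reporting sections. State in one sentence when ordinary AE inquiry starts.
2. Add a standard AE/SAE question to the coordinator's existing third-injection contact, with answers passed to the investigator, and a matching month 3 entry in Appendix 1. The contact can stay as it is, made to confirm the injection; no extra contact before the injection is needed.
3. In the safety tables, use the recorded onset date and time to list separately events that start before the first SV2 injection.

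**Cost:** a few entries in the schedule, one question in a contact that already takes place, and slightly more AE entry and coding. No visit, dose or clinical rule changes.

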- Early Discontinuation of Study Drug:**

- o A subject may be discontinued from study treatment at any time if the subject, the investigator, or the Sponsor feels that it is not in the subject’s best interest

to continue. The following is a list of possible reasons for study treatment discontinuation:

- Subject withdrawal of consent (or assent)
- Subject is not compliant with study procedures
- Adverse event that in the opinion of the investigator would be in the best interest of the subject to discontinue study treatment
- Protocol violation requiring discontinuation of study treatment
- Lost to follow-up
- Sponsor request for early termination of study
- Positive pregnancy test (females)

If a subject is withdrawn from treatment due to an adverse event, the subject will be followed and treated by the Investigator until the abnormal parameter or symptom has resolved or stabilized. All subjects who discontinue study treatment should come in for an early discontinuation visit as soon as possible and then should be encouraged to complete all remaining scheduled visits and procedures. All subjects are free to withdraw from participation at any time, for any reason, specified or unspecified, and without prejudice. Reasonable attempts will be made by the investigator to provide a reason for subject withdrawals. The reason for the subject's withdrawal from the study will be specified in the subject's source documents.

c. Analysis of Primary Endpoint:

d. For the primary endpoint, which is the change in VM-PATHI scores between month 1 and month 4 as compared between the galcanezumab arm and the placebo arm, a paired two-tailed Student's t-test will be used, provided the data is normally distributed. This will be conducted with an intent-to-treat analysis. Significance will be set at alpha of 0.05.

e. Analysis of Secondary Endpoints:

Definitive dizzy days/month, comparing baseline (month 0 to 1) to after treatment (month 3-4), between active treatment and control arms, will be assessed using a two-tailed t-test.

Response rates will be reported per category (100%, 75%, 50%, 25%, and 0% reduction in definitive dizziness days, comparing month 0 to 1 to month 3 to 4) for both active treatment and control arms. Number of subjects who experience 50% of better reduction in dizziness days will be compared using Chi Squared test.

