Dizziness Handicap Inventory will be compared between active treatment and control arms, looking at change in score from baseline to month 4, using a two-tailed t test.

PROMIS scores comparing active and placebo arm score changes from before (month 0) and after (month 4) treatment using a paired t-test.

Safety and tolerability data will be summarized by treatment group.

Adverse event rates will be coded by body system and MedDra classification term. Adverse events will be tabulated by treatment group and will include the number of patients for whom the event occurred, the rate of occurrence, and the severity and relationship to study drug.

Initially data will be summarized overall, by patient, and by treatment and control groups. Plots of each outcomes will be displayed graphically over longitudinal time points. Univariate summaries of all variables overall, by patient, and by subgroup will include means and standard deviations for continuous variables and counts and percentages for categorical variables.

Bias:

Bias will be minimized by using a double-blinded study design, with allocation concealment. This will limit selection, performance, and detection bias. In addition, this will help control for potential confounding variables. In addition, by including a placebo control group, we will minimize regression to the mean bias. Finally, by collecting information prospectively, we will minimize reporting bias.

Missing Data:

We will minimize missing data by having the clinical trial coordinator present to help the study subject fill out all data. We anticipate a 15-20% loss to follow up, and have accounted for that in our sample size calculations. Outliers and non-compliant subjects will be included in the analysis. We will perform an intent-to-treat analysis.

Trial Duration:

We estimate that this trial will take approximately 2 years to complete, once subject recruitment is able to begin. That includes 1.5 years for subject recruitment and data collection, and 6 months for closeout and data analysis. If recruitment is slower than expected, we will plan on keeping the trial open for a longer period of time. This seems unlikely based on our prior experience with recruitment in this patient population.

Pharmacy/Study Drug:

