The protocol and consent form will be reviewed and approved by the UCSF IRB prior to study initiation. Serious adverse experiences regardless of causality will be reported to the IRB in accordance with the standard operating procedures and policies of the IRB, and the Investigator will keep the IRB informed as to the progress of the study. The Investigator will obtain assurance of IRB compliance with regulations.

Data Analysis Plan:

Subjects will be divided by study status into several groups.

1. Per Protocol Analysis
 - a. Signed Consent
 - b. 4 study visits (in person or virtual) within:
 - i. SV2 (day 30) no earlier than day 23, and no later than day 44.
 - ii. SV3 (day 60/day 30 after SV2) no earlier than day 23 after SV2, and no later than day 37 after SV2.
 - iii. SV4 (day 120/day 60 after SV3) no earlier than day 50 after SV3, and no later than day 70 after SV3.
 - c. Received same drug (galcanezumab or placebo) for all doses during the trial
 - d. Completed Day 90 injection within 7 days of target date, so 23 to 37 days after SV3
 - e. 80% or better adherence to text message
 - f. Filled out all questionnaires
2. Intent to Treat
 - a. Everyone who signed consent and got at least one dose of study drug who does not meet per protocol criteria
3. SV2 failure
 - a. Signed consent but did not meet eligibility during the baseline month (less than 80% adherence to texting, or fewer than 4 definitive dizzy days or SV2 VM-PATHI less than 25)
4. SV1 failure
 - a. Signed consent but then VM-PATHI score too low on SV1
5. Screen failure
 - a. Did not meet inclusion/Exclusion so did not sign consent

Responsibilities of Study Team Members:

[name] (Principal Investigator): [name] is an Assistant Professor in the Department of Otolaryngology – Head and Neck Surgery, and the director of the Balance and Falls Center at UCSF. [name] will serve as PI for this project, and will supervise experimental design, data analysis, and summarizing the result for public disclosures to the academic community.

[name]: Co-investigator: [name] is an Assistant Professor of Neurology, and a member of the UCSF Headache Center. She will assist will all aspects of the study.

[name]: [name] is the director of the Headache Center at UCSF, and will assist in all aspects of the study.

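### The only written definition of the intent-to-treat group leaves out every protocol-compliant patient, and its dose requirement conflicts with the pharmacy section

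*Combined protocol and SAP*

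**What the plan says.** For the primary endpoint, Analysis of Primary Endpoint states: "This will be conducted with an intent-to-treat analysis". That section does not define the set.

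The only definition is in the Data Analysis Plan. It opens with "Subjects will be divided by study status into several groups" and lists five groups: per protocol, intent to treat, SV2 failure, SV1 failure and screen failure. Group 1 (per protocol) requires four visits within stated windows, the same drug at every dose, the day-90 injection on time, at least 80% text adherence, and "Filled out all questionnaires". Group 2 (intent to treat) is "Everyone who signed consent and got at least one dose of study drug who does not meet per protocol criteria".

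Four other places bear on who is analysed:

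- Missing Data: "Outliers and non-compliant subjects will be included in the analysis", followed by a further commitment to intent-to-treat.
- Pharmacy/Study Drug: "any failure of subjects to take the study drugs will just be considered a violation of protocol", and such patients are kept in the intent-to-treat analysis. No minimum dose is stated.
- Early Discontinuation of Study Drug: patients who stop treatment "should be encouraged to complete all remaining scheduled visits and procedures".
- Blinding: a patient unblinded in an emergency counts as a protocol violation and is removed from the study. What happens to that patient's data is not stated.

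**The concern.** Intent-to-treat ordinarily contains the per-protocol patients. Here the two are written as mutually exclusive, and the one named for the primary analysis is the one without the compliant patients. A programmer who followed item 2 exactly would compare the arms only among patients who were dosed and then departed from protocol.

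That is probably not what the authors intend. Even so, the text leaves the primary analysis set open: dosed non-compliers only, all dosed patients, or all randomised patients can each be read from it. In a trial of 50 patients a handful either way can move the result, so the choice should not remain open once allocation is known. The literal set would also be made up partly of patients lost to follow-up, who have no month-4 VM-PATHI score to contribute.

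**Working it through.** The question is mainly one of definition, so the first step is to set the texts against each other.

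**1. Three sets that can be read from the plan**

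| Reading | Basis | Compliant | Dosed, not compliant | Randomised, never dosed |
|---|---|---|---|---|
| Dosed non-compliers only | Data Analysis Plan item 2, literally | out | in | out |
| All dosed | groups 1 and 2 combined (stated nowhere) | in | in | out |
| All randomised | Pharmacy/Study Drug | in | in | in |

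Missing Data says that non-compliant patients are included, which presupposes a set already holding the compliant ones. It therefore does not fit the first row. Pharmacy/Study Drug sets no dose minimum and does not fit the first or second row.

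**2. Where a randomised, never-dosed patient goes**

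Randomisation follows confirmation of eligibility at SV2. A patient who then takes no injection fails group 1 (no day-90 injection), fails group 2 (no dose), and is not in groups 3 to 5, because eligibility was met. No group remains, yet Pharmacy/Study Drug keeps this patient in intent-to-treat.

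**3. Bound on the group sizes**

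Inputs: 50 patients. Planned loss is 10-20% (sample size justification in the summary), 10% (Sample Size) or 15-20% (Missing Data: "We anticipate a 15-20% loss to follow up"). A patient lost before SV4 cannot have four visits and all questionnaires, so cannot be per protocol. Assume the loss comes after the first dose.

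- Lower bound on group 2: 50 × 0.10 = 5; 50 × 0.15 = 7.5; 50 × 0.20 = 10.
- Upper bound on group 1: 50 − 5 = 45; 50 − 7.5 = 42.5; 50 − 10 = 40.

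Late visits or low text adherence would move more patients into group 2, by an amount the documents do not allow one to estimate.

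**4. Illustration of the literal reading**

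The plan states 90% power for a 7-point difference with 25 per arm at the 0.05 level, but gives no value for the SD. The figure therefore cannot be reproduced independently; one can only solve for the SD it implies. The plan names a paired test, but the arms hold different patients, so I used a two-sided two-sample t-test with noncentrality 7 / (SD × √(1/n₁ + 1/n₂)). The implied SD is 7.48: 7 / (7.48 × √(2/25)) = 3.31, giving 90%. At that SD, 45 patients give 86.6%, in line with the plan's claim of more than 80% after 10% dropout.

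Now assume, for illustration only, that group 2 holds 10 patients split 5 and 5, all with a month-4 score. The noncentrality is 7 / (7.48 × √(2/5)) = 1.48, and power is about 26%. With an SD of 10 the 50-patient and 10-patient figures are 68% and 16%; with an SD of 15 they are 37% and 10%. The 10-patient figures are generous, because patients lost to follow-up would have no score.

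**The case against.** The best reply is that item 2 is a status label and not an analysis-set definition. The list is introduced as a division by study status and runs down to people who never consented, and groups 3 to 5 cannot be analysis sets. In a mutually exclusive disposition list, group 2 naturally holds the dosed patients not already counted in group 1. This is a plausible account of what was meant. It does not repair the text: the list sits under the heading Data Analysis Plan, item 1 is titled as an analysis, item 2 carries the name of the primary analysis, and nothing says that the two are combined. If the list is only disposition, the plan has no definition of its primary set at all.

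On dosing, the reply is that the conflict is nearly empty in practice. Drug is handed out on the day of randomisation and the first two injections are monitored, so most failures would be missed later doses, and those patients meet the one-dose condition anyway. It may also be said that in a double-blind trial a set of randomised patients with at least one dose is defensible. Both points stand as to size. But the pharmacy text covers any failure to take drug and is not limited to later doses, so the two sections still disagree, and the disposition reading does not resolve that.

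It is also fair to say that the group-size bounds rest on planned dropout, that they and the power figures size only the literal reading, and that missing month-4 scores are a problem under any definition. The conflict with the primary-endpoint section alone rests on the usual meaning of intent-to-treat; the explicit clash is with Pharmacy/Study Drug, and next with Missing Data.

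**Conclusion.** The concern holds and should be fixed. As written, the definition removes all compliant patients from the analysis named as primary, and its dose condition contradicts another section. The literal reading is probably unintended, but no text in the plan rules it out in favour of a stated alternative.

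The number of patients affected cannot be derived. On planned dropout, and assuming loss after the first dose, at most 40-45 of 50 patients would be in the group left out and at least 5-10 in the literal intent-to-treat group. Between the two sensible readings, all dosed and all randomised, the difference should be small. The emergency-unblinding sentence is a lesser point: it needs clarifying because it is silent on data, while another kind of protocol violator is expressly kept in.

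**What to change.** In the Data Analysis Plan, before unblinding:

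- Define the intent-to-treat set as all randomised patients, analysed in the arm assigned, regardless of dosing, visit timing or adherence. Say what counts as randomised, since drug is labelled for individual patients before SV2 eligibility is confirmed.
- Remove the one-dose condition, so that this section agrees with Pharmacy/Study Drug.
- Make the per-protocol set a subset of intent-to-treat.
- Keep the five groups as a separate disposition table, with group 2 renamed and a place for randomised patients who were never dosed.

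In the blinding section, add one sentence stating that data from emergency-unblinded patients stay in the intent-to-treat analysis. This changes neither when unblinding is allowed nor how those patients are managed.

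The cost is a few sentences, with no new data collection.
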